6.6.9 Analysis Populations

Analysis populations are defined as follows:

- The Intent-to-Treat (ITT) population includes all randomized subjects, regardless of treatment received;
- The As Treated population includes all subjects who were randomized and treated with either PerClot or Arista, with subjects assigned to the treatment group for the treatment received (even if this differs from randomization assignment); and
- The Per Protocol population includes all subjects who were randomized and treated with either PerClot or Arista, and had no major protocol deviations, where major protocol deviations are defined as:
 - Failure to meet any preoperative inclusion/exclusion criteria;
 - Failure to meet any intraoperative inclusion/exclusion criteria; or
 - Any informed consent violation.

All efficacy analyses and summary statistics will be performed on the ITT, As Treated, and Per Protocol populations. Safety analyses will be performed on the ITT population.

No subject will be removed from the study once randomization occurs. All randomized subjects with available outcome data will be included in the analysis, according to the defined analysis population.

Study success will be evaluated on the As Treated population. Effectiveness analyses of the ITT and Per Protocol populations will be supportive of the As Treated analysis. Any clinically significant differences in effectiveness results between the analysis populations will be examined relative to protocol deviations and discussed.

6.6.10 Descriptive and Summary Statistics

Demographics, baseline characteristics, and the comparability of the PerClot and control group subjects will be assessed by tabulations of mean, median, range, standard deviation and analyses using t-tests of means or Wilcoxon tests for continuous factors. For categorical factors, frequency, percent and Fisher's exact tests of proportions will be carried out. Achievement of hemostasis for all treated bleeding sites will be assessed by tabulating frequency of success as a percentage and analyses using Chi-square test.

6.6.11 Covariate Analysis Methods

Covariate analyses will be performed to assess the association with certain study parameters on the primary efficacy endpoint. For these analyses, logistic regression models will be used. Covariates will be tested univariately for inclusion in the multivariate model. Covariate assessments may consist of, but are not limited to, the following variables:

- Demographic measures such as age, gender, ethnicity, and BMI;
- Medical history;
- Therapeutic area;
- Use of blood modifiers or products known to affect bleeding (including aspirin and colloids);
- Administrations of blood products;
- Fluids administered (including colloids and crystalloids);
- Surface area of the anatomic site;
- Initial bleeding severity (as continuous measure);
- Indication for surgery;
- Complete blood count and coagulation status;
- Complement C3;
- Smoking history;
- Use of oral contraceptives;
- Diabetes;
- Presence of any malignancies;
- Amount of hemostat applied;
- Core body temperature;
- Level of glycosylated hemoglobin;
- Other hemostatic efforts made;
- Procedure type;
- NNIS risk index;
- Blood glucose at randomization;
- Blood glucose within 1 hour of device application;

- American Society of Anesthesiologists Classification;
- Total operative time;
- Placement of wound drain;
- Drainage volume within 24 hours postoperatively;
- Total drainage volume;
- Total drainage duration; and
- Volume of fluid used to rinse away excess study device.

6.6.12 Poolability Analyses

It is expected that data will be poolable across trial sites and therapeutic areas, as all sites and Investigators will follow a common protocol with identical inclusion/exclusion criteria and defined objective efficacy parameters. Additionally, it is expected that data will be poolable across therapeutic areas. Potential variability in time to hemostasis between therapeutic areas is mitigated by limiting the types of procedures and bleeding severities for which subjects can be enrolled into the investigation.

Treatment effect will be evaluated by the proportion of subjects achieving hemostasis at 7 minutes by site, and again by therapeutic area. Each of these measures will be tested as a covariate in a logistic regression model, with the primary endpoint measure as the outcome. Additional logistic regression models will be fit to test treatment by site and treatment by therapeutic area interaction effects.

In the case that poolability across site or therapeutic areas is confirmed, as indicated by statistical significance at alpha > 0.15, the assumption of homogeneity will be accepted.

In the case that poolability across site or therapeutic areas is questionable, as indicated by statistical significance at alpha \leq 0.15, the assumption of homogeneity will be rejected. An additional primary efficacy analysis will be fit in order to ascertain the treatment effect after adjustment for site or therapeutic area. The reasons for any differences in outcome across these measures will be investigated and reported.

6.6.13 Missing Data

Every effort will be made to collect all data points in the study. The amount of missing data will be minimized by appropriate management of the clinical study, training of participating investigators and study coordinators, and sufficient monitoring of study sites. As the primary efficacy endpoint data is collected intraoperatively, missing data is expected to be minimal, and subject withdrawal and loss to follow-up during the follow-up period is not expected to impact the efficacy analysis.

To assess the impact of missing data on the primary endpoint, a sensitivity analysis will be conducted. The primary endpoint analysis will be repeated under two scenarios: one in which all missing endpoints are assumed to be successes for the PerClot group and failures for the control group, and another in which all missing endpoints are assumed to be failures for the PerClot group and successes for the control group. If these scenarios do not impact the conclusion of the analysis, then the impact of missing data will be considered inconsequential. The reason for any significant differences between scenarios will be investigated and reported.

6.7 Data Collection and Data Management

The handling of data will comply with regulatory guidelines and the Sponsor or Sponsor representative's SOPs and work instructions. Data management activities specific to this study will be described in a Data Management Plan. All steps and actions taken regarding data management and quality assurance will be documented in the Sponsor representative's SOPs and data handling guidelines.

Data will be collected via electronic data capture (EDC) screens referred to as eCRFs, designed specifically for this investigation. The Principal Investigator at each investigational site will review and approve all completed eCRFs.

Data collected must be supported by source documents found at the site, and subject medical records, hospital charts, operative reports, laboratory and diagnostic testing results, office visits, source document worksheets as supplied by the Sponsor, etc. will be utilized for the collection of relevant data. Completed eCRFs will undergo 100% source documentation verification and will be checked visually by the study monitor for completeness and consistency.

Electronic data queries will be created for identified errors on eCRFs that have been submitted to ensure errors/omissions are corrected. New and previous findings and recommended corrective and preventative actions, if they exist, will be communicated with the study staff during monitoring visits, and will also be addressed in a final letter that will be sent to the Investigator after each monitoring visit.

6.7.1 Data Retention

Clinical investigation records will be stored in a confidential manner so as to protect the confidentiality of subject information.

All correspondence related to this clinical investigation will be kept in appropriate investigational files. Records of subjects, source documents, eCRFs, device inventory, IRB and Sponsor correspondence, and Investigator correspondence pertaining to the investigation must be kept on file. All original subject, laboratory, and device inventory records (electronic and/or hard copies) relating to this investigation (to include the Informed Consent document, research records and data, and research specimens) shall be retained for no less than 2 years after the latter of the following dates: the date on which the investigation is terminated, the date on which the investigation is completed, or the date that records are no longer required for the purposes of supporting the pre-market approval expansion application (PMA). The Sponsor shall be contacted prior to the destruction of any records pertaining to this investigation to ensure that they no longer need to be retained. The Sponsor must approve the destruction of any investigational records.

6.7.2 Study Audits

The Sponsor, the Sponsor representative, and the reviewing IRB may audit the study centers and regulatory authorities may inspect any study center to evaluate the conduct of the study. Such audits will require access to all study records, including source documents for inspection and comparison with the eCRFs. Subject privacy must, however, be respected. Sufficient prior notice will be provided to allow the Investigator to prepare properly for the audit. The Investigator should immediately notify the sponsor if they have been contacted by a regulatory agency concerning an upcoming inspection.

6.8 Protocol Amendments and Deviations

Amendments to this clinical investigation protocol will be identified by protocol reference number and amendment number. All amendments will be accompanied by a title page that identifies the changes being made and the protocol section(s) affected. The protocol reference number and amendment number will be placed on the title page and every subsequent page of an amendment.

A protocol amendment will not be implemented before all necessary reviews and approvals have been obtained, including Sponsor approvals, Investigator signatures, and IRB approvals, as applicable.

7 Statement of Compliance

FDA regulations (21 CFR Parts 50, 54, 56, and 812) and ICH E6 Good Clinical Practices (GCP), as recognized by FDA, are being followed in the conduct of this clinical investigation.

This clinical investigation shall not begin until the required approvals are obtained from the IRB and all applicable regulatory authorities.

Subjects will not be paid to participate in the clinical trial. However, reasonable travel expenses may be reimbursed; the reimbursement amount will be subject to respective IRB approvals. It is not expected that subjects will incur any additional cost due to their participation in the trial.

If a subject experiences a medical emergency and has followed the directions of the Investigator or other study staff, and if the Sponsor determines that the emergency is related to PerClot, the Sponsor will pay for whatever emergency care is required.

8 Informed Consent Process

All subjects must voluntarily provide signed informed consent prior to receiving any pre-investigation assessments that would not have been performed as part of normal subject care. Informed consent must be obtained in accordance with FDA regulations 21 CFR Part 50, 45 CFR Part 46 and ICH E6 Good Clinical Practices (GCP), as recognized by FDA. Also see Section 6.3.1.

9 Adverse Events

9.1 Adverse Event Definitions

An adverse event is any untoward medical occurrence in a clinical study subject. An adverse event would be any unfavorable or unintended sign, symptom, or disease that appears or worsens during the clinical study regardless of the relationship to the device. Adverse events will be collected for all subjects after they are enrolled in the trial.

An abnormal laboratory value is clinically significant if the investigator determines that it requires treatment, or if he/she would collect the laboratory value at a later date to verify normalization.

A serious adverse event (SAE) is an adverse event which results in any of the following outcomes:

- Death;
- A life-threatening adverse event;
- Inpatient hospitalization or prolongation of existing hospitalization;
- A persistent or significant disability or incapacity or substantial disruption of the ability to conduct normal life functions;
- A congenital anomaly or birth defect; and/or;
- Other, as determined by the investigator.

An unanticipated adverse device effect (UADE) is any serious adverse effect on health or safety or any life-threatening problem or death caused by, or associated with, a device, if that effect, problem, or death was not previously identified in nature, severity, or degree of incidence in the investigational plan or application (including a supplementary plan or application), or any other unanticipated serious problem associated with a device that relates to the rights, safety, or welfare of subjects.

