- c. A score of 2 denotes slight bleeding. The rate of bleeding is slightly faster than oozing. There is no pulsatile flow present. This is what one may expect from capillary, venular, or arteriolar bleeding.
- d. A score of 3 denotes moderate bleeding. There may be a weak pulsatile flow present. If there is a pulsatile flow, the rate of blood flow is similar to the rate of flow for a score of 2. If there is no pulsatile flow, the rate of blood flow is faster than slight bleeding.
- e. A score of 4 denotes severe bleeding. For the most part, pulsatile flow is present. If there is no pulsatile flow, then the rate of blood flow is extremely rapid.
- f. A score of 5 denotes life-threatening bleeding. A strong pulsatile flow is always present and the rate of blood flow is extremely rapid.

Intraoperative Exclusion Criteria

- Subject undergoing a cardiac procedure in which there is no aortic anastomosis or aortotomy suture line to evaluate using the bleeding severity scale (i.e., not for treatment at the distal coronary artery bypass graft anastomosis);
- Subject in whom any major intraoperative bleeding incidences during the surgical procedure occurred (i.e., subject with assignment of an American College of Surgeons Advanced Trauma Life Support Hemorrhage Class of II, III, or IV Hemorrhage)^x;
- Subject who has an active or potential infection at the surgical site, or whose surgical wound is defined as a wound classification of CO (Contaminated) or D (Dirty or Infected) based upon the Center for Disease Control and Prevention's wound classification system;^{ix}
- Subject who has undergone platelet receptor GP IIb/IIIa antagonist therapy less than 48 hours prior to surgery.

Investigators will be trained on bleeding severity assessment and the appropriate application of PerClot and the control device prior to the enrollment of any subjects.

[figure not shown]
All patients presenting to the investigator for elective (non-emergent) surgical procedures are potential study candidates and should be screened for eligibility. Subjects who do not meet all eligibility criteria will not be enrolled.

Enrollment occurs when a subject meets the preoperative inclusion/exclusion criteria, signs the ICF, meets the intraoperative eligibility criteria, and is randomized to a treatment arm.

6.3.3 *Subject Randomization*

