This information will be recorded on the Preoperative eCRF and Laboratory eCRF. The Blood Modifiers/Blood Sugar Lowering eCRF should be completed as applicable.

6.4.3 *Intraoperative Procedures and Evaluations*

All subjects will undergo the same intraoperative investigational evaluations unless otherwise stated. Intraoperative is defined as the time interval from when the subject enters the surgical suite until the subject exits the surgical suite.

6.4.3.1 *Surgical Procedures*

Subjects undergoing the following elective open, surgical procedures will be eligible for investigation enrollment:

- Cardiac procedure (Epicardium)
- Cardiac procedure (Aortic Anastomosis or Aortotomy Suture Line);
- Liver resection;
- Total splenectomy;
- On-clamp partial nephrectomy; or
- Radical nephrectomy.

For each of these procedures, a bleeding site meeting intraoperative inclusion/exclusion criteria and whose anatomic site is less than or equal to 25cm² and whose anatomic application site is less than or equal to 47cm², will be evaluated for bleeding flux and satisfaction of the intraoperative eligibility criteria.

For each of these procedures, PerClot should not be allowed to enter into cell saver devices, extracorporeal cardiopulmonary bypass circuits or autologous blood salvage circuits. Granules of PerClot or fragments of gelled PerClot may pass through 40 micron transfusion filters of blood salvaging systems.

For cardiac procedures, the site of evaluation for satisfaction of intraoperative eligibility criteria will be any bleeding sites on the epicardium, along an aortic anastomotic suture line, or an aortotomy suture line. For example, the surgeon will perform dissection of adhesions per his or her conventional methods and bleeding will be controlled using means continually employed by the surgeon prior to surgical closure. Prior to application along an aortic anastomotic suture line or an aortotomy suture line, suture line gaps \geq 2mm and large needle holes \geq 2mm will be ligated prior to assessment of intraoperative eligibility criteria. Any bleeding site on the epicardium, or along an aortic anastomotic suture line, or an aortotomy suture line meeting the eligibility criteria will be evaluated for satisfaction. PerClot should be applied after drug reversal and the patient is taken off by-pass.

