9.2 Assessing Adverse Events

Adverse events will be documented by the Investigator on the appropriate source document(s) at the investigational site and will also be recorded onto the Adverse Event eCRF. All adverse events will be monitored until they are adequately resolved or explained.

Adverse events are to be recorded and dated according to when they are first observed. The respective treatment(s) should also be documented. An event should be recorded on the eCRF only once unless there are multiple occurrences of that event. As an example, a stroke reported once with sequelae still present at subsequent visits should not be reported again. However, a second stroke should be reported on a second eCRF.

The following should be determined and recorded on the Adverse Event eCRF:

- Accepted medical term for the event;
- Description of the event;
- Duration of the event (dates of onset and resolution);
- Outcome;
- Severity of the event;
- The relationship of the event to the investigational device or the control device;
- Description of the action taken; and
- Determination of whether or not the event was a serious adverse event.

All procedure complications/adverse events through final follow-up will be reported and graded as per Common Toxicity Criteria for Adverse Events (2009): CTCAE-2009.²²

The CDRH guidance for adverse event data will be followed.
(www.fda.gov/ForIndustry/DataStandards/StudyDataStandards/default.htm)

The severity of the event will be graded as follows by the Investigator:

- Grade 1: Mild; asymptomatic or mild symptoms; clinical or diagnostic observations only; intervention not indicated;

- Grade 2: Moderate; minimal, local or noninvasive intervention indicated; limiting age-appropriate instrumental activities of daily living;
- Grade 3: Severe or medically significant but not immediately life-threatening; hospitalization or prolongation of hospitalization indicated; disabling; limiting self-care activities of daily living;
- Grade 4: Life-threatening consequences; urgent intervention indicated; or
- Grade 5: Death related to AE.

Every effort should be made to determine the cause of each adverse event, since a judgment must be made as whether or not it is related to the investigational device or comparator device. The relation to PerClot or control hemostatic device will be graded and recorded on the Adverse Event eCRF by the Investigator using the following definitions:

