The state produced by the establishment of an infective agent in or on a suitable host. The Centers for Disease Control and Prevention's wound classification system is as follows: Clean [Class C (I), an uninfected operative wound in which no inflammation is encountered and the respiratory, alimentary, genital, or uninfected urinary tracts are not entered] and Clean-contaminated [Class CC (II), operative wounds in which the respiratory, alimentary, genital, or urinary tracts are entered under controlled conditions and without unusual contamination] are allowed. Contaminated [Class CO (III), open, fresh, accidental wounds, operations with major breaks in sterile technique or gross spillage from the gastrointestinal tract, and incisions in which acute, nonpurulent inflammation is encountered are included in the category.] and Dirty or Infected (Class D (IV) old traumatic wounds with retained devitalized tissue and those that involve existing clinical infection or perforated viscera] will be excluded.

Inflammatory and Immune Responses

The reaction of the body to foreign material mediated through the blood supply.

Informed Consent (IC)

The voluntary verification or a patient's willingness to participate in a clinical trial, along with the documentation thereof. This verification is requested only after complete, objective information has been given about the trial, including an explanation of the objectives, potential benefits, risks and inconveniences, alternative therapies available, and of the subject's rights and responsibilities.

Informed Consent Form (ICF)

A written document that contains relevant information about the clinical investigation and that is signed and dated by the subject.

Injury to Normal Tissue

Cellular necrosis or damage.

INR

International Normalized Ratio – a calculated made to standardize prothrombin time.

Institution or Site

Location of research. Retains ultimate responsibility for human subject regulation compliance.

Institutional Review Board (IRB)

An independent body consisting of medical professionals and non-medical members responsible for reviewing and providing initial and continuing approval of research in human subjects and verifying that the safety, integrity, and human rights of subjects participating in a particular clinical investigation are protected.

Intraoperative

Skin incision to skin closure.

Investigator

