- h. Device damaged prior to use (FDA Source Code 2284)
- i. Inability to irrigate (FDA Source Code 1337)
- j. Inaccurate delivery (FDA Source Code 2339)
- k. Occlusion (obstruction or blockage) within device or device component (FDA Source Code 2423)

 1 Yes	 0 No
 1 Yes	 0 No
 1 Yes	 0 No
 1 Yes	 0 No
 1 Yes	 0 No
 1 Yes	 0 No
 1 Yes	 0 No
 1 Yes	 0 No
 1 Yes	 0 No
 1 Yes	 0 No
 1 Yes	 0 No
 1 Yes	 0 No

l. Other, please specify:

*Please include FDA
Source Code*

*Device malfunctions will be reported using nomenclature specific to devices per the FDA Center for Devices and Radiological Health Event Reporting webpage: <http://www.fda.gov/MedicalDevices/Safety/ReportaProblem/EvenProblemCodes/ucm/134751.htm>.

INTRAOPERATIVE ADVERSE EVENTS

75. Did any complications/adverse events occur intraoperatively?

1 Yes *If yes, please complete the Adverse Event Form.*
 0 No

76. Please list any known intraoperative deviations to the protocol:

0 Not applicable

77. Additional comments:

0 Not applicable

/ / /

Principal Investigator Signature

Date (DD/MMM/YYYY)

Subject Initials: Subject Number: Visit Date (DD/MMM/YYYY): / / Visit Type: 4 Postoperative

POSTOPERATIVE ASSESSMENT

1. Does the subject have clinical signs or symptoms of bleeding?

1 Yes *If yes, please complete the Adverse Event Form.*
 0 No

2. Did the subject undergo a reoperation?

1 Yes *If yes, please complete the Reoperation Form.*
 0 No

3. Blood products administered postoperatively: Blood Product Units

 1 None	Red Blood Cells	 
	Platelets	 
	Fresh Frozen Plasma	 
	Cryoprecipitate	 

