14. Albumin	 g/dL	 1	 1 Yes	 0 No	 1 Yes*  0 No
15. HbA1c	 %	 1	 1 Yes	 0 No	 1 Yes*  0 No
16. C3	 mg/dL	 1	 1 Yes	 0 No	 1 Yes*  0 No
17. Blood Glucose [†]	 mg/dL	 1	 1 Yes	 0 No	 1 Yes*  0 No

Note: Blood glucose measurement should be evaluated by a venous blood draw or Nova StatStrip blood glucose meter.

Preoperative Lab work will occur no more than 1 month (30 days) prior to surgery.

Please complete the Adverse Event Form after device application only.*[†]Blood glucose levels should be collected within 1hr (\pm 30 minutes) after device application, 6 hours (\pm 30 minutes), 12 hours (\pm 30 minutes), 24 hours (\pm 30 minutes).**

Reoperation DRAFT Form
Form 10Form completed by: _____
Date form completed: ___ / ___ / ___Subject Initials: Subject Number: Surgery Date (DD/MMM/YYYY): / / Visit Type: 9 Reoperation

PROCEDURE INFORMATION

1. Reason for reoperation:
2. Procedure(s) performed: a.
b.
c.
3. Was this reoperation for hemostatic agent application site bleeding?
 1 Yes
 0 No
 - a. If yes, methods used to attempt to obtain hemostasis (check all that apply):
 1 Not applicable
 2 Make-up stitches (# of stitches:)
 3 Other, please specify:
4. Was the hemostatic device visually apparent?
 1 Yes, please comment:
 0 No

Please complete the Adverse Event Form for all Reoperations.

Principal Investigator Signature

 / /

Date (DD/MMM/YYYY)

Adverse Event DRAFT Form
Form 11A

Form completed by: _____
Date form completed: ___ / ___ / ___

Subject Initials: Subject Number:

ADVERSE EVENT

1. Description of adverse event:

2. CTCAE-2009* short name for adverse event: 3. Date of onset (DD/MMM/YYYY): / /

4. Severity of adverse event (per CTCAE-2009* grade):

- 1 Grade 1 - Mild; asymptomatic or mild symptoms; clinical or diagnostic observations only; intervention not indicated

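### Surgical events from before randomization can enter the adverse event data, and neither the forms nor the SAP separate them from later Day 0 events

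*Protocol*

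**What the plan says.** **Start of collection.** Protocol Section 9.1: "Adverse events will be collected for all subjects after they are enrolled in the trial". Under Section 6.3.2 a subject is enrolled once he or she has met the preoperative criteria, signed consent, "meets the intraoperative eligibility criteria, and is randomized to a treatment arm". The Glossary agrees. Randomization follows conventional hemostasis and the bleeding flux measurement (6.4.3.2 and 6.4.3.3), so it comes well into the operation.

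**What is asked for.** Section 6.4.3.5 lists the incidence of complications and adverse events among the data to be collected intraoperatively. Item 75 of the Operative Form (Appendix E), repeated on the Operative Worksheet (Appendix F), asks: "Did any complications/adverse events occur intraoperatively". A yes leads to the Adverse Event Form. Section 6.4.3 states: "Intraoperative is defined as the time interval from when the subject enters the surgical suite until the subject exits the surgical suite". The Glossary has "Skin incision to skin closure".

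**What is recorded about onset.** Section 9.2 requires "Duration of the event (dates of onset and resolution"), which are dates only. The Adverse Event Form has the field "Date of onset (DD/MMM/YYYY") and no clock time.

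**What is analysed.** SAP 4.4.4 reports adverse event incidence by type. It compares arms with Fisher's exact tests for serious device-related events, unanticipated adverse device effects (UADEs), and events with at least 5% overall incidence, all in the ITT population. It gives no rule on onset. It also says that the safety analyses are descriptive and carry no formal hypothesis tests.

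**The concern.** The question asked at the operation covers a wider period than Section 9.1 allows. An injury during dissection and an event after device application both fall on the day of surgery. Both can reach the same form, with the same onset date.

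The device cannot have caused an event that preceded randomization. Such events are balanced between arms in expectation, so counting them does not favour one arm on average. They do add the same background to both arms and so make a real excess of harm harder to see. In a safety comparison, that shift toward no difference is the unwelcome direction.

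**Working it through.** **1. Order of events on the day of surgery.** Entry to the surgical suite, skin incision, resection or repair, conventional hemostasis, flux measurement, randomization, device application, closure, exit. Section 9.1 starts at randomization. Item 75 starts at suite entry or skin incision, depending on the definition of intraoperative. Under either definition the period between that start and randomization is asked about, although Section 9.1 does not collect it.

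**2. Whether the record restores the order.** The Operative Form times device application to the second but has no field for the time of randomization. The Adverse Event Form has the date only. The Operative Worksheet, which Section 6.4.3.5 makes the source document for intraoperative evaluations, has the same gap. Free text may show the order for some events; no structured field does.

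**3. Which analyses are exposed.**

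- Serious device-related events: the possible, probable and definite grades in Section 9.2 each require a temporal relationship to device use. An event before application does not meet them, so this comparison is largely protected.
- UADEs: Section 9.1 requires that the effect be caused by or associated with a device, so this comparison is largely protected too.
- Frequent adverse events and the incidence tables: no relatedness condition and no onset condition, so these are exposed.

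**4. Illustration of the dilution.** The documents give no adverse event rates and no power for these comparisons, so there is no plan figure to reproduce. The one plan number used is 162 per arm (Protocol 6.6.5, SAP 4.2.1.1).

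Let p be the true incidence of an event type after randomization, and q the share of each arm with an event of that type before randomization, taken as independent of later events. Then

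observed rate = 1 − (1 − p)(1 − q), and observed difference = (1 − q) × true difference.

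For p = 5% and q = 10%: 1 − 0.95 × 0.90 = 14.5%. For p = 15% and q = 10%: 1 − 0.85 × 0.90 = 23.5%. The difference is 0.90 × 10 = 9.0 points. Exact power of the two-sided 0.05 Fisher test, with p and q assumed:

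| q in both arms | Observed, true 5% vs 15% | Power | Observed, true 10% vs 20% | Power |
|---|---|---|---|---|
| 0 | 5.0% vs 15.0% | 0.82 | 10.0% vs 20.0% | 0.67 |
| 5% | 9.8% vs 19.3% | 0.63 | 14.5% vs 24.0% | 0.53 |
| 10% | 14.5% vs 23.5% | 0.49 | 19.0% vs 28.0% | 0.43 |
| 20% | 24.0% vs 32.0% | 0.32 | 28.0% vs 36.0% | 0.30 |

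With no true difference (10% in both arms), the test rejects 3.1% to 3.8% of the time for q from 0 to 20%. Equal recording therefore does not create false signals.

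**5. The 5% threshold.** A type at 3% after randomization and 3% before shows 1 − 0.97 × 0.97 = 5.9%. It would be tested as frequent although its incidence after randomization is below 5%.

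**The case against.** **The forms are only samples.** Appendix E says that the actual layout may differ, and Section 9.1 read strictly excludes earlier events. This rules out the stronger reading that pre-randomization complications do enter the arm comparison; the text shows only that they can. It does not remove the point, because Section 6.4.3.5 and the dates-only rule in Section 9.2 are protocol body text.

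**There are further conflicting start points.** A reader might take the Laboratory Form instruction, "Please complete the Adverse Event Form after device application only", as another start rule. That form serves preoperative, postoperative and unscheduled visits, and the glucose value drawn between randomization and application goes on the Operative Form. The instruction in effect screens out preoperative values. A reader might also count the two definitions of intraoperative, but both begin before randomization, so unifying them would not close the gap.

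**The whole-operation question is intended.** Procedure complications are a safety endpoint listed separately from adverse events (Protocol 6.1.3 and 6.6.4, SAP 4.4.4), and item 75 serves both. This stands. Narrowing item 75 to events since randomization could lose complications that the protocol means to count.

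**The comparison is descriptive and the rates are assumed.** This stands. The trial was not sized for these tests. The assumed q must hold within one event type, and several listed types, such as adhesions or cancer recurrence, are unlikely to arise before randomization in the same operation. Subjects with Class II to IV hemorrhage or with contaminated or dirty wounds are excluded before randomization. A type lifted over 5% gains a comparison; that hides nothing.

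**The events could be sorted out later.** There is a free-text description, a relatedness grade and 100% source verification. It would be too strong to say that earlier events can never be removed. But source verification cannot supply an onset time that the source worksheet does not ask for.

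**Bias between arms.** A reader might infer it, because only subjects are blinded and recording could differ by arm. Nothing in the documents shows that it would.

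**Conclusion.** The point holds in limited form. Section 9.1 and the whole-operation collection in Section 6.4.3.5 and item 75 do not match. Onset is recorded by date only, and SAP 4.4.4 has no onset rule. Events that the device cannot have caused can therefore be counted in the frequent adverse event comparison and the incidence tables, where they dilute any difference between arms. The serious device-related and UADE comparisons are largely protected.

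The fall in power from 0.82 to 0.32 shows the direction and possible scale of the dilution. It rests on assumed incidences, an assumed rate before randomization that is equal in both arms, and independence of earlier and later events. It is not an estimate for this trial, and the SAP does not treat these comparisons as formal tests. Primary efficacy is not affected. The change is worth making because it is cheap and because timing not captured at entry may be hard to recover.

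**What to change.** 1. Keep item 75 as a question about the whole operation, so that procedure complications are still captured.
2. On the Adverse Event Form, add for Day 0 events one box with three choices: before randomization; after randomization but before application; after application.
3. In SAP 4.4.4, state that adverse event incidence and the arm comparisons, including the 5% threshold for frequent events, count only events with onset at or after randomization. List earlier events separately, as procedure complications where applicable.

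Randomization is the suitable anchor. It agrees with Section 9.1 and exists for every ITT subject, whereas application does not: Section 6.4.3.3 foresees subjects who die between the two.

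The cost is one form field, one SAP rule and one extra listing.
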